7.0 Data and Specimen Banking – N/A

This study does not involve the banking of specimens or long-term data storage for future unrelated research.

8.0 Sharing of Results with Subjects*

Study results relating to the participant's individual subsidence measurements or clinical outcomes may be shared at their discretion. This will be done privately and confidentially; results of any other participants will not be shared.

9.0 Study Timelines*

Each participant will be involved in the study for approximately 1 year, from the time of surgery through standard postoperative care. Data will be collected at preop, 6 weeks, 6 months, and 1-year post-op, coinciding with already scheduled clinic visits. The anticipated amount of time to enroll all subjects is 1 year, with the total duration of the project estimated to be 2 years.

10.0 Inclusion and Exclusion Criteria*

Potential participants will be identified from the MedStar Orthopaedic Surgery clinics at MGUH and MWHC. Screening will occur during routine preoperative consultation visits for patients scheduled to undergo primary, uncemented THA due to osteoarthritis or other non-inflammatory degenerative joint disease.

Patients will be screened by the study investigator or trained research coordinator. Screening will involve review of the EMR for clinical and radiographic eligibility,

MOD00024127

Page 9 of 18

Revised: November 12, 2025 IRB Approved

12/18/2025 - 11/3/2026

PROTOCOL TITLE: Comparison of clinical and radiographic results of collared and collarless femoral stems in total hip arthroplasty

verification of surgical plan, preoperative radiographic assessment, and assessment of patient capacity to provide informed consent. Patients who meet all inclusion criteria and none of the exclusion criteria will be approached for informed consent and formally enrolled after confirming eligibility.

Inclusion Criteria:

- Adults (≥ 18 years old) scheduled for primary, uncemented THA using a cementless femoral stem.
- Diagnosis of primary osteoarthritis or other non-inflammatory degenerative joint disease.
- Ability and willingness to comply with study procedures and follow-up schedule.
- Ability to provide written informed consent.

Exclusion Criteria:

PROTOCOL TITLE: Comparison of clinical and radiographic results of collared and collarless femoral stems in total hip arthroplasty

- **Patients not indicated for a cementless THA.**
 - Prior surgery on the ipsilateral hip (e.g., prior THA, internal fixation, osteotomy).
 - Use of cemented or hybrid femoral components.
 - Revision THA or conversion THA.
 - Active or prior infection of the hip joint.
 - Severe osteoporosis (T-score ≤ -2.5) or known metabolic bone disease.
 - Inability to complete follow-up or anticipated relocation out of the area.

Special Populations:

The following special populations will be excluded from participation in this study: adults unable to provide consent, anyone under the age of 18, and pregnant women.

11.0 Vulnerable Populations* - N/A

12.0 Local Number of Subjects

For this study we aim to enroll 100 participants (50 per group) undergoing primary, cementless THA across two MedStar sites, MedStar Georgetown University Hospital and MedStar Washington Hospital Center. All participants will be screened at the time of surgical scheduling and enrolled if they meet the criteria and consent to participate. This target number of 100 participants accounts for any dropouts throughout the study. Based on our power calculation (assuming 80% power, significance of 0.05, and a SD of 0.45 mm based on prior studies), a sample size of at least 20 subjects per group (40 in total) would be needed to complete the research procedures.

13.0 Recruitment Methods

Recruitment will occur during standard preoperative clinic visits at the Department of Orthopedic Surgery at MGUH and MWHC. Potential subjects will be identified weekly by IRB-approved research staff by screening clinic appointments. Patients scheduled for primary, uncemented THA will be approached during these visits. Recruitment will begin after IRB approval and continue until the target enrollment of 100 participants is reached. Each potential participant will be approached in-person by a study investigator or trained research coordinator prior to surgery, typically 2–4 weeks in advance.

The study will be described in detail, and eligible patients will be provided with a written informed consent form and ample time to ask questions. If interested, they may sign the consent form at that time or take it home and return it during a subsequent visit. Patients may also choose to complete an electronic consent form

MOD00024127

Page 11 of 18 Revised: November 12, 2025 IRB Approved

12/18/2025 - 11/3/2026

PROTOCOL TITLE: Comparison of clinical and radiographic results of collared and collarless femoral stems in total hip arthroplasty

that can be sent to their emails through a secure MedStar consenting platform, Interlace.

All subjects will be under the routine clinical care of orthopaedic providers at the study institution and will be recruited without deviation from the standard clinical pathway for surgical planning and follow-up. Recruitment will occur entirely through face-to-face interaction during clinic visits, with no use of public advertisements, social media, or media broadcast. No posters or flyers regarding the study will be distributed.

No monetary compensation will be provided to participants for their involvement in this study.

14.0 Withdrawal of Subjects*

A subject may choose to withdraw from the study at any time. Withdrawal of a subject will have no effect on their clinical care or clinical decision making.

Subjects may also be withdrawn from the study without their consent under the following circumstances:

- Intraoperative change in surgical plan, such as conversion to a cemented or hybrid femoral stem, revision THA, or significant intraoperative complications rendering the assigned study implant unusable.
- Failure to attend postoperative follow-up appointments necessary for primary or secondary outcome data collection.
- Medical conditions or complications (e.g., infection, stroke, malignancy) that significantly impact the participant's ability to safely continue study participation or follow the protocol.
- Protocol violation identified by the research team that invalidates study participation (e.g., unintentional enrollment of an ineligible subject).

In all such cases, the reason for withdrawal will be documented in the subject's research file and medical record.

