2.0 Objectives*

SA1: Prospectively assess clinical outcomes in patients undergoing primary total hip arthroplasty with a collared versus collarless femoral stem of the same design.

SA2: Evaluate serial radiographs to quantify differences in subsidence between collared and collarless implant groups.

SA3: Report and compare incidence rates of intraoperative and postoperative periprosthetic fractures and aseptic loosening following primary total hip arthroplasty with use of either a collared or collarless stem.

Hypothesis: The addition of a collar to the same designed triple-taper primary hip stem will lead to a reduction in subsidence and incidence of perioperative and periprosthetic femur fractures.

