Perhaps most compelling is the growing body of evidence linking collared stems to reduced femoral stem subsidence—an early indicator of mechanical instability and a predictor of later aseptic loosening. A randomized controlled trial using radiostereometric analysis (RSA) found that collared stems exhibited significantly less subsidence than collarless stems at two weeks postoperatively (mean difference 2.23 mm; $p = 0.023$), although the difference diminished by one year. Additional studies using non-invasive EBRA (Ein-Bild-Röntgen-Analyse) confirm that collared stems consistently demonstrate lower average subsidence over 6 to 18 months.

Despite promising preliminary data, several gaps in the literature persist. For example, intraoperative PPFs are typically treated intraoperatively and may lead to a change in the femoral component type that is utilized. Often, this is not captured in retrospective reviews or during chart assessment even with prospectively collected data. Such arguments support the necessity of a controlled, prospective study directly comparing collared and collarless stems with standardized measurement of femoral stem subsidence and documentation of associated complications such as aseptic loosening and PPF. Furthermore, the clinical significance of early migration differences observed with various imaging modalities has not been fully elucidated, nor has their correlation with long-term outcomes been firmly established.

This proposed randomized controlled trial seeks to address these gaps by comparing the clinical and radiographic outcomes of collared versus collarless femoral stems in THA, using femoral stem subsidence as the primary endpoint and incidence rates of PPF, aseptic loosening, and PROMs as key secondary endpoints. By employing standardized radiographic measurements and robust follow-up, this study will offer high-quality evidence to inform implant selection and optimize surgical outcomes. It will also contribute to the development of clinically relevant thresholds for subsidence that can serve as early predictors of implant failure.

References:

<https://doi.org/10.1016/j.jor.2024.01.013>

MOD00024127

Page 4 of 18

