6.0 Procedures Involved*

This study is a prospective, randomized controlled trial comparing the clinical and radiographic outcomes of a collared versus collarless femoral stems of the same design in primary THA. A total of 100 participants undergoing elective, uncemented primary THA for degenerative hip disease will be enrolled.

Participants will be randomized in a 1:1 ratio to receive either a collared femoral stem or a collarless femoral stem. All patients indicated for a cementless primary total hip arthroplasty will be offered enrollment. Once consented, they will be randomized into the collared or collarless stem groups. Study participants will be informed about the risk of randomization due to removing the elements of choice from the clinician, as outlined in the informed consent form.

MOD00024127

Page 6 of 18

Revised: November 12, 2025 IRB Approved

12/18/2025 - 11/3/2026

PROTOCOL TITLE: Comparison of clinical and radiographic results of collared and collarless femoral stems in total hip arthroplasty

The primary endpoint is femoral stem subsidence, measured at postoperative 6week, 6-month, and 1-year clinical visits, which coincide with standard of care routine follow-up. Secondary endpoints include the incidence of PPF and aseptic stem loosening within the first postoperative year. Again, all research procedures are designed to align with standard perioperative and postoperative care for THA, minimizing burden for study participants. Additionally, the ACTIS Hip Stem (DePuy Synthes, Warsaw, IN) is routinely used by the participating surgeons for the last 3-4 years. The following outlines the specific protocol steps and time points:

Preoperative (Day -30 to 0):

- Obtain written informed consent either in person or via Interlace.
- Confirm eligibility criteria (inclusion/exclusion).
- Record baseline demographic data, diagnosis, and Dorr classification (from preop imaging).
- Randomization and group assignment.

Operative Day (Day 0):

- THA performed using the allocated femoral stem type (collared or collarless), via a standard surgical approach.
- Per standard practice, intraoperative documentation of any complications, including intraoperative PPFs, will be recorded by the surgical team.

Postoperative Follow-Up:

- Routine anterior-posterior (AP) pelvic and lateral hip X-rays will be obtained at 6 weeks, 6 months, and 1 year.

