 - Electronic medical records (EMR)
 - Operative reports
 - Imaging records (X-rays)
 - Clinic visit notes
- Patient-reported outcome forms—collected in OBERD, the standard platform at MedStar for collecting PROMs

Data Collected:

- Demographics and clinical variables: age, sex, BMI, comorbidities, Dorr classification.
- Operative data: stem type, surgical approach, intraoperative complications.
- Primary endpoint: femoral stem subsidence at 6 weeks, 6 months, and 1 year, measured in millimeters from standardized serial radiographs.
- Secondary endpoints:
 - PPF incidence (confirmed radiographically or operatively).
 - Aseptic loosening (evidenced by radiolucent lines, implant migration, or revision surgery).
- Other outcomes: functional scores (PROMs), adverse events, and reoperation rates.

MOD00024127

Page 8 of 18

Revised: November 12, 2025 IRB Approved

12/18/2025 - 11/3/2026

PROTOCOL TITLE: Comparison of clinical and radiographic results of collared and collarless femoral stems in total hip arthroplasty

Data Collection Methods:

- Radiographic analysis performed by independent reviewers blinded to group allocation.
- Adverse events recorded by research staff at each visit and during any interim visits.

Long-Term Follow-Up — Patients will follow standard protocol for follow-up, offering the possibility of more longitudinal reporting potentially 5-10 years postop.

Humanitarian Use Device (HUD) — N/A

This study does not involve any HUDs. All devices used (collared and collarless femoral stems) are FDA-approved for standard use in primary THA and do not require an Investigational Device Exemption (IDE). The 510(k) number for the collared hip stem is K150862 and for the collarless version is K21058.

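### Section 14.0 lets the team withdraw a randomized patient when an intraoperative fracture makes the assigned stem unusable, although that fracture is an SA3 endpoint and SA3 needs one year of follow-up

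*Protocol*

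**What the plan says.** Section 6.0 places randomization in the preoperative period, so every patient who reaches surgery already belongs to an arm.

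Section 14.0 introduces its list of team-initiated withdrawals with "Subjects may also be withdrawn from the study without their consent under the following circumstances". The first ground is a change of plan during surgery, and the examples given are "conversion to a cemented or hybrid femoral stem, revision THA, or significant intraoperative complications rendering the assigned study implant unusable". On what happens next, the section says "In all such cases, the reason for withdrawal will be documented", in the research file and the medical record. It does not say whether follow-up continues or whether later data may be used.

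Three other places bear on this rule:

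- Section 3.0 (Background) states that "intraoperative PPFs are typically treated intraoperatively and may lead to a change in the femoral component type that is utilized", and gives the poor capture of this event elsewhere as a reason for doing the trial.
- Section 2.0 (SA3) sets out to report and compare "incidence rates of intraoperative and postoperative periprosthetic fractures and aseptic loosening". The hypothesis also names perioperative fracture.
- Section 6.0 gives the time window: "Secondary endpoints include the incidence of PPF and aseptic stem loosening within the first postoperative year".

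On recording and blinding, section 6.0 says for the operative day that "intraoperative documentation of any complications, including intraoperative PPFs, will be recorded by the surgical team", and under data collection methods "Radiographic analysis performed by independent reviewers blinded to group allocation". No one else is described as blinded.

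**The concern.** The first ground in section 14.0 does not name fracture, but a fracture that makes the assigned stem unusable falls squarely within it, and section 3.0 makes the connection itself. The protocol therefore permits a patient to leave the study after randomization because of an event that is one of its own endpoints. The trial's hypothesis is that the event is less common with a collar. If that is right, such withdrawals would be expected to differ between arms.

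The rule is discretionary, and those who apply it can know both the arm and the outcome. At stake are the one-year SA3 rates and the patient-reported outcomes for exactly the patients whom the Background says other studies lose. Fractures treated with the assigned stem kept in place, and fractures after surgery, are outside this ground.

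**Working it through.** The protocol gives no figure on this point. Its only calculation is the sample size for subsidence: 2 × (1.96 + 0.84)² × 0.45² / 0.4² ≈ 19.8, or 20 per group. That reproduces but does not bear on this question.

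**Following one patient through the text**

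1. The patient is randomized before surgery (section 6.0).
2. A fracture occurs during surgery and the assigned stem cannot be used (a possibility stated in section 3.0).
3. The fracture is recorded on Day 0 (section 6.0). It is an SA3 event (section 2.0).
4. The team may withdraw the patient from the study (section 14.0).
5. From then on the only stated obligation is to document the reason. Assessments at 6 weeks, 6 months and 1 year are no longer assured for research, although SA3 runs for a year (section 6.0).
6. Section 17.0 compares fracture and loosening between arms without saying whether a withdrawn patient remains in the comparison.

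Steps 1 to 3 are sound. The gap is in steps 4 to 6.

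**How sparse the events are**

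As an assumption, take the 90-day fracture rates cited in section 3.0, 0.4% collared and 1.6% collarless, with 50 per arm (section 12.0). They are not rates of stem-changing intraoperative fracture and serve only for scale.

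- Expected fractures: 50 × 0.004 = 0.2 and 50 × 0.016 = 0.8, a total of 1.0.
- Probability of none in either arm: 0.996^50 × 0.984^50 = 0.818 × 0.446 = 0.365.
- Probability of two or fewer in total: 0.365 + 0.370 + 0.185 ≈ 0.92.
- Weight of one event: 1/50 = 2.0 percentage points of an arm's rate, against a cited between-arm difference of 1.6 − 0.4 = 1.2 points.

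**Whether a significance verdict could turn on it**

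With no fracture in the other arm, Fisher's exact test gives p = 0.056 for 5/50 and p = 0.027 for 6/50, so at least six fractures in one arm are needed. At the assumed rates, the probability of p < 0.05, summed over all outcomes, is about 0.0001. Significance is not the issue; the reported rates are.

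**Share of an arm without one-year data**

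If 1, 2 or 3 patients in an arm were withdrawn on this ground (assumed range): 1/50 = 2%, 2/50 = 4%, 3/50 = 6%. Each could lose all three scheduled assessments.

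**The case against.** The best case for leaving the text alone has five parts.

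- **The fracture is not lost.** It is recorded by the surgical team and the withdrawal reason is documented. This stands. An analysis plan could keep it in the count.
- **A patient who has already fractured counts once, so a later fracture changes nothing, and SA3 concerns collared or collarless stems, so loosening of a replacement stem may fall outside it.** This has some force if incidence is counted once per patient. But SA3 names intraoperative fracture, postoperative fracture and loosening as separate items. A patient whose stem is changed for a reason other than fracture has no Day 0 event to count. Reoperation and patient-reported outcomes are affected whichever way incidence is counted.
- **The later data will exist anyway.** Withdrawal does not alter clinical care, visits and imaging are routine, and patient-reported outcomes sit on the institution's standard platform. This is largely true, and it is why the remedy is cheap. But nothing says the study goes on collecting or using those records after withdrawing someone, and an analysis plan cannot supply data not collected for research.
- **Analysis sets belong in the statistical analysis plan, which is not shown.** That holds for an unstated analysis population. Here the protocol states a rule on who remains in the study.
- **Selective withdrawal is conjecture.** The rule is permissive, and a surgeon necessarily sees whether the stem has a collar. This stands in part: lack of blinding does not show bias, only that discretion is exercised without that protection. Also, at the assumed rates three or more collarless fractures of any kind have a probability of about 4.6%, so the 6% figure is near the extreme if fracture is the only cause.

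**Conclusion.** The concern holds. A stated rule permits removal after randomization on grounds that can depend on both arm and outcome, and it can end the one-year data that SA3 requires. This should be fixed.

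The size and direction of any bias are unknown, because the protocol gives no rate of stem-changing fracture. On an assumed 1 to 3 withdrawals, 2% to 6% of an arm would lack one-year SA3 and patient-reported data. That matters mainly because about one fracture is expected in the whole trial at the cited rates, so each affected patient carries weight in the reported rates. The primary subsidence comparison is not the concern, and no significance verdict is likely to depend on it. The conclusion rests on the wording of sections 2.0, 3.0, 6.0 and 14.0; the borrowed rates only illustrate scale.

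**What to change.** Amend the first ground in section 14.0 to say that:

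1. An intraoperative fracture or a change of stem is recorded as an endpoint or intercurrent event and is not by itself a reason to withdraw the patient from data collection.
2. The fracture counts in the randomized arm, whichever stem is implanted.
3. Routine-care data on fracture, loosening, reoperation and patient-reported outcomes continue to be collected and are analysed as randomized unless the patient withdraws consent. Only the subsidence measurement ends once a non-study stem is in place.

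The other withdrawal grounds are untouched, and no rule on surgical management is proposed.

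The cost is two or three sentences in the protocol. Visits, imaging and the patient-reported platform are already in routine use, so no extra visits or patients are needed. The small downside is that a few patients with a non-study stem and no subsidence value stay in the denominators.

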19.0 Provisions to Protect the Privacy Interests of Subjects

The following steps will be taken to respect and protect the privacy interests of all participants:

- Recruitment and consent discussions will occur in private clinic rooms during routine preoperative visits. Discussions will be conducted in a quiet, confidential setting to ensure that participants are comfortable and not overheard by others.
- Personal and health-related information will be obtained only by authorized research staff who are trained in HIPAA and human subjects research protections. Subjects will be informed that their participation is entirely voluntary and that they may decline to answer any questions or withdraw at any time without affecting their care.
- Only the minimum necessary identifiable information will be collected to achieve the study aims.
- Identifiers will be removed or replaced with coded subject IDs during data analysis and publication to prevent disclosure of personal information.

To help subjects feel comfortable and reduce any sense of intrusiveness during research interactions:

- Study procedures are designed to align with routine clinical care, minimizing additional burden or deviation from normal patient experiences.
- The research team will introduce themselves clearly, explain the purpose of the study, and emphasize that participation is optional and will not affect their surgical care or relationship with providers.
- Written and verbal information will be provided in clear, respectful language. Ample time will be given for questions.
- Subjects will be reminded that they can decline to answer any questions or stop participation at any time.
- Follow-up assessments rely on clinical imaging and observations already performed as part of standard care, eliminating the need for sensitive questioning or intrusive examinations.

The research team will access subject information through the following authorized and IRB-approved means:

- MedConnect (EMR): Used to review demographic data, surgical details, imaging, clinical outcomes, and follow-up attendance.
- Study-Specific Forms and Surveys: Any forms collected directly from subjects will be securely stored and managed by the study team. Access will be limited to IRB-approved personnel listed on the protocol, and all team members will be trained in HIPAA compliance and institutional data security protocols.

MOD00024127

Page 15 of 18 Revised: November 12, 2025 IRB Approved

12/18/2025 - 11/3/2026

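### Section 14 lets the team withdraw randomised patients for missed visits or disabling complications, and nothing in the protocol provides for their outcomes to be collected afterwards

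*Protocol*

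**What the plan says.** Protocol section 14.0 opens its list of team-initiated withdrawals with "Subjects may also be withdrawn from the study without their consent under the following circumstances". Three of the four grounds matter here.

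- **First bullet (in theatre):** it includes "significant intraoperative complications rendering the assigned study implant unusable".
- **Second bullet (after surgery):** "Failure to attend postoperative follow-up appointments necessary for primary or secondary outcome data collection".
- **Third bullet (after surgery):** "Medical conditions or complications (e.g., infection, stroke, malignancy) that significantly impact the participant's ability to safely continue study participation or follow the protocol".

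The section then states that "the reason for withdrawal will be documented in the subject's research file and medical record", and, for withdrawals generally, "Withdrawal of a subject will have no effect on their clinical care or clinical decision making". It says nothing about outcome data after withdrawal, and no other section does.

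Section 4.0 makes subsidence at 6 weeks, 6 months and 1 year the primary endpoint, with periprosthetic fracture, aseptic loosening and patient-reported outcomes as secondary endpoints. Section 6.0 adds "Other outcomes: functional scores (PROMs), adverse events, and reoperation rates". It also has fractures and loosening found from clinical assessment, imaging and surgical reports. Section 19.0 gives the team access to the electronic medical record (EMR): "Used to review demographic data, surgical details, imaging, clinical outcomes, and follow-up attendance".

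**The concern.** The section does not separate stopping study procedures from stopping observation. Once the stem is implanted there is no study treatment to discontinue, the films are routine care, and clinical care is unaffected by withdrawal. What withdrawal mainly takes away is the patient's research data.

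The grounds can be related to outcome. A patient may miss a visit because of a hip problem, and a serious complication may itself be an adverse event or lead to a reoperation, both of which the trial records. The study hypothesis is that fractures are less frequent with a collar. If complications lead to missed visits or withdrawal, the losses could therefore differ by arm. The decision is discretionary, and section 6.0 states blinding to allocation only for the radiographic analysis.

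At stake are the counts of fracture, loosening and reoperation, and the later subsidence values of patients who would have come back. A statistical analysis plan cannot repair this, because it cannot recover data that were never collected.

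**Working it through.** **1. The plan's own figure, and whether power is at risk.** Inputs from section 17.0: difference 0.4 mm, SD 0.45 mm, 80% power, alpha 0.05 (taken as two-sided).

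- n per arm = 2 × (1.96 + 0.842)² × (0.45 / 0.4)² = 19.9, rounded up to 20. The stated 20 per group is reproduced. An exact t-test calculation gives 20.9, that is 21 per arm.
- At 50 per arm, power is about 99%.
- 100 enrolled against 40 needed tolerates 1 − 40/100 = 60% loss.

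Power for subsidence is therefore not threatened by this rule.

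**2. How many patients the second bullet could reach.** Assumption: each of the three visits is missed independently with probability m. The Protocol gives no rate, so a range is shown. The share missing at least one visit is 1 − (1 − m)³.

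| m per visit | Miss at least one, so open to withdrawal | Lack the 1-year film if a miss is simply missing |
|---|---|---|
| 5% | 14% | 5% |
| 10% | 27% | 10% |
| 15% | 39% | 15% |

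These are upper limits under the assumption, since the rule permits withdrawal and does not require it. Even 39% loss leaves 61 patients, above the 40 needed.

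**3. How few events there are.** Section 3.0 cites 90-day fracture rates of 0.4% (collared) and 1.6% (collarless). With 50 per arm:

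- collared: 50 × 0.004 = 0.2
- collarless: 50 × 0.016 = 0.8
- total: 1.0 expected fracture in 100 patients

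**4. What outcome-related withdrawal does to a rate.** Let w be the share withdrawn and r the event risk in withdrawn patients relative to retained patients. Both are assumed; the Protocol gives neither. For a true risk p:

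- share of events lost = w·r / (1 − w + w·r)
- rate seen in retained patients = p / (1 − w + w·r)

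| w | r | Events lost | A true 1.6% is seen as |
|---|---|---|---|
| 5% | 1 | 5% | 1.6% |
| 10% | 3 | 25% | 1.3% |
| 10% | 5 | 36% | 1.1% |
| 20% | 5 | 56% | 0.9% |

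With r = 1 events are lost but the rate in retained patients is unbiased. Bias needs withdrawal to be related to outcome, and bias between arms needs that relation, or the amount of withdrawal, to differ by arm.

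**5. The first bullet beside SA3.** SA3 (section 2.0) compares intraoperative as well as postoperative fractures. Section 3.0 observes that an intraoperative fracture may change the component used and often goes uncaptured in other studies. Section 6.0 has such fractures recorded on the operative day. Section 14.0 then allows the patient to be withdrawn if the complication makes the assigned stem unusable, and does not say whether that fracture still counts.

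**The case against.** A reader might infer that section 14.0 ends safety follow-up in the very patients most likely to have the counted events. The Protocol does not support that.

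- **The rule is permissive and silent.** Nothing says that event data stop or that collected data are discarded. Section 6.0 also has any clinically indicated imaging or intervention reviewed for endpoint classification, so ascertainment is not tied only to scheduled visits. The consent form, which may address data use after withdrawal, was not available for this review. This stands: what can be shown is a permission to withdraw with no provision to continue.
- **Higher risk is not shown.** No document links missed visits, infection, stroke or malignancy to fracture or aseptic loosening. Infection is not a named endpoint; it enters only as an adverse event or through reoperation. This stands, and is why r is an assumption above.
- **The third bullet is qualified.** A complication alone is not a ground; it must significantly impair safe participation or adherence. This stands, and the investigator's discretion there has a purpose.
- **The fracture comparison is weak anyway.** With 50 per arm, Fisher's exact test gives p = 0.056 for 5 against 0 fractures and p = 0.027 for 6 against 0. One lost fracture is unlikely to decide a test. It would still distort the incidence that SA3 sets out to report.
- **Record review is imperfect.** An event treated outside the health system may not appear in its EMR. True, but incomplete capture is better than none.

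What the objection does not answer is that the Protocol, having the means to keep observing these patients, does not say that it will.

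**Conclusion.** The point holds as a weakness in the withdrawal rule that should be corrected. Section 14.0 permits discretionary withdrawal after randomisation, on grounds that can be related to outcome, and no section provides for outcome collection to continue.

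The harm is possible bias and lost rare events, not lost power. Under independent misses at 5% to 15% per visit, 14% to 39% of patients could be withdrawn under the second bullet, against 5% to 15% who would lack the 1-year film if a miss were simply recorded. About 1 fracture is expected in 100 patients at the cited 90-day rates, which cover less than the 1-year follow-up. The size and direction of any bias between arms cannot be derived from the Protocol. The stronger statements, that follow-up does end or that withdrawn patients are at highest risk, go beyond the text.

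**What to change.** In section 14.0:

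1. Remove a missed visit as a ground for withdrawal. Record it as a missing visit, with the participant staying in the study.
2. Leave the investigator's discretion to stop study procedures for medical reasons as it is.
3. Add wording for all team-initiated withdrawals, for example: *Unless the participant withdraws consent for data use, fracture, loosening, reoperation and adverse events will be collected from available records through 1 year, any later routine film will be measured, and the participant will be analysed in the randomised group.*
4. State that this covers the first bullet too, so that an intraoperative fracture that makes the assigned stem unusable is still counted for SA3.

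The cost is a few sentences in the Protocol, a matching edit to the consent form, and some EMR review for non-attenders. EMR access is already in place and the films are standard care, so no new visits are needed. The sample size does not change.
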